5.2 Trial Treatment(s)

The treatment(s) to be used in this trial are outlined below in Table 5.

Table 5 Trial Treatment

Dose/ Potency	Drug	Dose	Route of Administration	Treatment Period ⁶	Use
Placebo Run-in (all	Matching placebo for	0.1 mL QD	Subcutaneous	0.1 mL ¹ QD for 2 weeks	experimental (trial drug)
treatment groups)	MK-8521 180 μg, 1.0mL Vial A				
	Matching placebo for MK-8521 300 µg, 1.0mL Vial B	0.1 mL QD	Subcutaneous	0.1 mL ¹ QD for 2 weeks	experimental (trial drug)
MK-8521 180 μg Group	MK-8521 180 μg 0.6 mg/mL, 1.0mL Vial C	0.1 mL QD to 0.3 mL QD	Subcutaneous	Days 1-6: 0.1 mL ¹ QD Days 7-13: 0.2 mL ² QD Days 14-84: 0.3 mL ³ QD	experimental (trial drug)
	Matching placebo for MK-8521 300 μg, 1.0mL Vial D	0.1 mL QD to 0.5 mL QD	Subcutaneous	Days 1-6: 0.1 mL ¹ QD Days 7-13: 0.2 mL ² QD Days 14-20: 0.3 mL ³ QD Days 21-84: 0.5 mL ⁴ QD	experimental (trial drug)
MK-8521 300 μg Group	Matching placebo for MK-8521 180 μg, 1.0mL Vial C	0.1 mL QD to 0.3 mL QD	Subcutaneous	Days 1-6: 0.1 mL ¹ QD Days 7-13: 0.2 mL ² QD Days 14-84: 0.3 mL ³ QD	experimental (trial drug)
	MK-8521 300 μg 0.6 mg/mL, 1.0mL Vial D	0.1 mL QD to 0.5 mL QD	Subcutaneous	Days 1-6: 0.1 mL ¹ QD Days 7-13: 0.2 mL ² QD Days 14-20: 0.3 mL ³ QD Days 21-84: 0.5 mL ⁴ QD	experimental (trial drug)

Protocol/Amendment No.: 004-02

Dose/ Potency	Drug	Dose	Route of Administration	Treatment Period ⁶	Use
Placebo	Matching	0.1 mL QD	Subcutaneous	Days 1-6: 0.1 mL ¹ QD	experimental
Group	placebo for	to 0.3 mL		Days 7-13: 0.2 mL ² QD	(trial drug)
	MK-8521	QD		Days 14-84: 0.3 mL ³ QD	
	180 μg,				
	1.0mL				
	Vial C				
	Matching	0.1 mL QD	Subcutaneous	Days 1-6: 0.1 mL ¹ QD	experimental
	placebo for	to 0.5 mL		Days 7-13: 0.2 mL ² QD	(trial drug)
	MK-8521	QD		Days 14-20: 0.3 mL ³ QD	
	300 μg,			Days 21-84: 0.5 mL ⁴ QD	
	1.0mL				
	Vial D				
Liraglutide	liraglutide	0.6 mg QD	Subcutaneous	Days 1-6: 0.6 mg QD	active-
Group –	6 mg/mL ⁵	to 1.8 mg		Days 7-13: 1.2 mg QD	comparator
Open-Label		QD		Days 14-84: 1.8 mg QD	

- 1. Equivalent to 10 Units in an insulin syringe.
- Equivalent to 20 Units in an insulin syringe.
- 3. Equivalent to 30 Units in an insulin syringe.
- ^{4.} Equivalent to 50 Units in an insulin syringe.
- 5. Liraglutide will be supplied locally by the trial site.
- ⁶. Treatment periods are approximate. See Section 6.0 for allowable visit windows.

The first dose of trial treatment will be administered at the trial site at Visit 3/Randomization (Day 1). All doses taken at scheduled clinic visits will be administered by the subject as a witnessed dose. Subsequent dosing will be performed once daily by the subject (i.e., unsupervised at his/her home) at approximately the same time each day.

All supplies indicated in Table 5 above will be provided centrally by the Sponsor or locally by the trial site, subsidiary or designee, depending on local country operational or regulatory requirements.

For any commercially available product that is provided by the trial site, subsidiary or designee every attempt will be made to source these supplies from a single lot/batch number. The trial site will be responsible for recording the lot number, manufacturer and expiry date of any locally purchased product.

The investigator shall take responsibility for and shall take all steps to maintain appropriate records and ensure appropriate supply, storage, handling, distribution and usage of trial treatments in accordance with the protocol and any applicable laws and regulations.

5.2.1 Dose Selection/Modification

5.2.1.1 Dose Selection (Preparation)

The rationale for selection of doses to be used in this trial is provided in Section 4.0 – Background & Rationale. There are no specific calculations or evaluations required to be performed in order to administer the proper dose to each subject.

5.2.1.2 Dose Escalation of Investigational Product

MK-8521 or MK-8521 Placebo Treatment Groups

Subjects randomized to MK-8521 or MK-8521 placebo will begin the trial (**Visit 3/Day 1**) on 0.1 mL from each vial (60 µg/day for subjects randomized to active MK-8521).

At **Visit 4/Day 7**, the dose should be increased to 0.2 mL from each vial (120 μ g/day for subjects randomized to active MK-8521).

At Visit 5/Day 14, the dose should be increased to 0.3 mL from each vial (180 μg/day for subjects randomized to active MK-8521).

At **Visit 6/Day 21**, the dose from the MK-8521 300 μ g vial (labelled Vial D) should be increased to 0.5 mL/day (300 μ g/day for subjects randomized to the MK-8521 300 μ g treatment group).

Note the following related to the dose escalation:

- The dose escalation regimen for MK-8521 may be modified by the investigator to appropriately manage observed GI intolerance. Specifically, the investigator may decide to delay one scheduled dose increase for up to 7 days based upon tolerability (e.g., GI adverse events).
- The dose from both vials of MK-8521 or MK-8521 placebo must reach 0.3 mL/day (180 μ g/day for subjects randomized to active MK-8521) by Day 21.
- The dose from Vial D should reach 0.5 mL/day (300 µg/day for subjects randomized to the MK-8521 300 µg treatment group) by Day 28.
- Subjects who cannot tolerate 0.5 mL/day from Vial D may continue in the trial on 0.3 mL/day (180 μ g/day for subjects randomized to active MK-8521) from each vial.
- No dose changes are allowed beyond Day 28.
- See Table 6 for guidance on dose escalation.
- •An asymptomatic increase in HR that does not meet discontinuation criteria (Section 5.9) should not delay dose escalation.

The rationale for this dose escalation regimen can be found in Section 4.2.2.1.

Protocol/Amendment No.: 004-02

Table 6 Dose Escalation for Subjects Randomized to MK-8521 or Placebo

Vial	Visit 3/ Day 1	Visit 4/ Day 7	Visit 5/ Day 14	Visit 6/ Day 21	Visit 7/ Day 28
MK-8521 180 μg or matching placebo ¹ Vial C	initiate 0.1 mL/day	increase to 0.2 mL/day	increase to 0.3 mL/day ³	continue 0.3 mL/day ³	continue 0.3 mL/day ³
MK-8521 300 μg or matching placebo ¹ Vial D	initiate 0.1 mL/day	increase to 0.2 mL/day	increase to 0.3 mL/day ³	increase to 0.5 mL/day ^{2,3}	If any step is delayed, the final dose of 0.5 mL/day must be reached at Visit 7/Day 28 ^{2,3}

The investigator may delay one step of the dose escalation by one week; however, the dose from each vial must reach 0.3 mL/day no later than Day 21.

Liraglutide Treatment Group

Subjects randomized to open-label liraglutide will begin the trial (Visit 3/Day 1) on 0.6 mg/day liraglutide.

At Visit 4/Day 7, the dose of liraglutide should be increased to 1.2 mg/day.

At Visit 5/Day 14, the dose of liraglutide should be increased to 1.8 mg/day.

The titration regimen for liraglutide may be modified to appropriately manage observed GI intolerance. The liraglutide dose should be titrated to the full target dose (1.8 mg/day) no later than Day 21. Subjects who cannot tolerate the 1.8 mg/day dose of liraglutide may continue in the trial on the 1.2 mg/day dose.

5.2.2 Timing of Dose Administration

On days without a clinic visit, MK-8521 300 μ g, MK-8521 180 μ g, or matching MK-8521 placebo SC injections; or open-label liraglutide will be administered in the morning at approximately the same time each day. Background metformin is to be taken as prescribed by their primary care physician. MK-8521 or matching placebo injections will be administered SC in the abdominal wall. The injection site should be rotated within the abdominal wall area.

On the days of clinic visits, subjects will take their investigational product, as well as background metformin, after all study procedures are completed.

At Visit 2/Week -2, subjects will enter a single-blind placebo run-in period. Subjects will be taught how to self-administer and will be expected to perform self-administration of the single-blind placebo SC injections during the 2-week single-blind placebo run-in period in preparation for the double-blind dosing period.

Subjects who cannot tolerate the 0.5 mL/day dose from **Vial D** may continue on a dose of 0.3 mL/day from each vial.

Subjects who cannot tolerate at least 0.3 mL/day from each vial should be discontinued (See Section 7.1.4.1).

Protocol/Amendment No.: 004-02

At **Visit 3/Day 1,** MK-8521 300 μ g, MK-8521 180 μ g, or matching MK-8521 placebo SC injections, or open-label liraglutide will be administered (see Section 4.2.2.1 for initial doses and Section 5.2.1.2 for dose escalation) by the subject as a witnessed dose after the completion of study procedures. Background metformin should be taken after all study procedures are completed. Investigational site staff should assure that the administration technique is appropriate, and provide additional training on study drug administration, as necessary.

Subjects will be asked to bring the remaining investigational product (used and unused vials/pens) to the clinic for review at each scheduled visit.

5.2.3 Trial Blinding/Masking

A double-blind/masking technique will be used. MK-8521 and placebo will be packaged identically so that blind/masking is maintained. The subject, the investigator and Sponsor personnel or delegate(s) who are involved in the treatment or clinical evaluation of the subjects are unaware of the group assignments.

The liraglutide treatment arm will be open-label therefore, the Sponsor, investigator and subject will know the treatment administered.

See Section 7.1.4.2, Blinding/Unblinding, for a description of the method of unblinding a subject during the trial, should such action be warranted.

5.3 Randomization or Treatment Allocation

Randomization will occur centrally using an interactive voice response system / integrated web response system (IVRS/IWRS). There are 4 treatment arms. Subjects will be assigned randomly in a 1:1:1:1 ratio to MK-8521 300 μ g, MK-8521 180 μ g, MK-8521 matching placebo, or open-label liraglutide, respectively.

5.4 Stratification

Randomization will be stratified according to the following factors:

- 1. A1C*: <8.5% or $\ge 8.5\%$
- 2. BMI*: $<30 \text{ kg/m}^2 \text{ or } \ge 30 \text{ kg/m}^2$
- 3. AHA washout status: yes or no.

*The Visit 1/Screening value will be used for stratification if Visit 2/Week -2 occurs ≤2 weeks of Visit 1/Screening. The Visit 2/Week -2 value will be used for stratification if Visit 2/Week -2 is >2 weeks after Visit 1/Screening (this will include all subjects undergoing AHA washout).

5.5 Concomitant Medications/Vaccinations (Allowed & Prohibited)

Medications or vaccinations specifically prohibited in the exclusion criteria are not allowed during the ongoing trial. If there is a clinical indication for any medication or vaccination specifically prohibited during the trial, discontinuation from trial therapy or vaccination may be required. The investigator should discuss any questions regarding this with the Sponsor Clinical Director. The final decision on any supportive therapy or vaccination rests with the

Protocol/Amendment No.: 004-02

investigator and/or the subject's primary physician. However, the decision to continue the subject on trial therapy or vaccination schedule requires the mutual agreement of the investigator, the Sponsor and the subject.

AHAs taken by the subject at any time prior to Visit 1/Screening, and any other medications taken within 8 weeks of Visit 1/Screening, should be recorded on the appropriate electronic case report form (eCRF). The site may rely on subject report for this information. Concomitant medications taken during the trial must also be recorded. Subjects should be questioned about their use of concomitant medications at the time points indicated in the Trial Flow Chart — Section 6.0. Subjects should be instructed to contact the study investigator before initiating any prescription or non-prescription medications during study participation. If medical necessity requires initiation of a medication prior to discussion with the study investigator, the subject should communicate with the study investigator as soon as possible.

Prohibited Medications

Medications listed below are prohibited while subjects are receiving investigational product during the treatment period (see Section 5.9 - Subject Withdrawal/Discontinuation from Treatment Criteria):

- 1. All Antihyperglycemic Medications: with the exception of background metformin ≥1000 mg/day) and double-blind (MK-8521 or placebo) or open-label (liraglutide) study medication.
- 2. Corticosteroids: Treatment for ≥14 consecutive days or repeated courses of pharmacologic doses of corticosteroids.

Note: Inhaled, nasal, and topical corticosteroids and physiological replacement doses of adrenal steroids are permitted.

3. Weight-loss Medications: Treatment with or initiation of a weight-loss medication (e.g., orlistat, phentermine, topiramate, lorcaserin) is prohibited (see Section 5.1.3).

Note: Subjects who are on treatment with other medication(s) associated with weight changes (e.g., anti-psychotic agents) and who are weight-stable (i.e., <5% change in body weight within 6 months of **Visit 1/Screening**) at **Visit 1/Screening** are eligible to participate in the study and permitted to continue these medications during the trial.

4. Beta Blockers: Treatment with or initiation of a beta blocker is prohibited.

Note: Systemic and ophthalmic beta blockers are prohibited.

- 5. Marijuana: Legal (including medicinal marijuana use) or illegal use is prohibited.
- 6. Medications with sympathomimetic activity: Treatment with or initiation of medications with sympathomimetic activity (e.g. pseudoephedrine, phenylpropanolamine, inhaled albuterol, methylphenidate) is prohibited

Protocol/Amendment No.: 004-02

Guidance for Other Medications

The investigator or subject's physician/health care provider is permitted to make adjustments in the subject's non-AHA therapies throughout the trial if clinically warranted. Guidance for specific medications which are permitted during the study is provided below.

- 1. All subjects must be on a stable dose of metformin (≥1000 mg/day metformin IR or metformin XR) for ≥12 weeks prior to randomization.
- 2. Acetaminophen and NSAIDs may be used for minor ailments (e.g. minor injuries, osteoarthritis, upper respiratory tract infections) without prior consultation with the Sponsor Clinical Monitor. Individual acetaminophen doses should be 500 mg or less, with a total daily dose of 2000 mg or less.
- 3. Blood Pressure and Lipid-lowering Medications: Concomitant lipid-lowering medications are permitted. Antihypertensive medications with the exception of betablockers are permitted. It is preferable that doses of these medications remain stable during the double-blind treatment period.
- 4. Hormonal Replacement Therapy: Hormone replacement therapy are permitted, but subjects should be on stable regimens, and are expected to remain on their stable regimen while receiving blinded investigational product during the double-blind treatment period and for 14 days after the last dose of blinded investigational product.
- 5. Thyroid Hormone Replacement Therapy: Thyroid replacement medication (e.g., thyroxine) is permitted, but subjects should be on a stable dose for at least 6 weeks prior to **Visit 1/Screening**. Subjects who meet the TSH exclusion criterion specified in Table 3 may be re-screened after being on a stable thyroid replacement regimen for at least 6 weeks.
- 6. Nicotine/Nicotine products: The use of nicotine containing products is prohibited during the trial and for 14 days after the last dose of investigational product. This includes but is not limited to: cigarettes, cigars, pipes, smokeless tobacco, e-cigarettes and nicotine replacement therapies (nicotine patches, gum, inhalers, nasal sprays, topical gels, and lozenges).
- 7. Supplements and/or Traditional Medicines: The use of herbal supplements and other natural products should be discouraged. Subjects who do not discontinue the use of such supplements prior to **Visit 2/Week -2** should be instructed not to change the use or dose of the supplement during the trial. Subjects should be instructed not to initiate new supplements during the trial.

5.6 Rescue Medications & Supportive Care

No rescue or supportive medications are specified to be used in this trial.

Protocol/Amendment No.: 004-02

5.7 Diet/Activity/Other Considerations

5.7.1 Diet

Subjects will be seen by a dietician or qualified healthcare professional for dietary and exercise counseling.

For subjects who **do not** require AHA washout, initial dietary and exercise counseling will occur at **Visit 2/Week -2.**

For subjects who do require AHA washout, initial dietary and exercise counseling will occur at **Visit 1A** prior to the initiation of washout.

The subject will receive counseling on diet consistent with the American Diabetes Association.

At each subsequent visit, the subject's diet should be monitored, and counseling provided, as appropriate. Detailed dietary information will not be captured.

5.7.2. Alcohol, Caffeine and Tobacco

- Subjects will be counseled to limit alcohol use to moderate amounts (i.e., ≤1 drinks per day and no more than 7 drinks per week). One alcoholic drink is defined as 5 oz. (150 mL) of wine, or 12 oz. (350 mL) of beer, or 1.5 oz. (50 mL) of 80-proof liquor.
- Ingestion of caffeine will be prohibited for at least 10 hours prior to scheduled ECGs, HR and blood pressure determinations.
- Nicotine-containing products are prohibited during the trial.

5.7.3 Activity

Subjects will be counseled to maintain a medically appropriate, routine exercise program and consistent physical activity level during the trial. Subjects must not engage in physically strenuous exercise (for example: heavy lifting, weight training, calisthenics, and aerobics) within 48 hours before each blood sample collection for clinical laboratory tests for the duration of participation in the trial.

5.8 Subject Withdrawal/Discontinuation Criteria

Subjects may withdraw consent at any time for any reason or be dropped from the trial at the discretion of the investigator should any untoward effect occur. In addition, a subject may be withdrawn by the investigator or the Sponsor if enrollment into the trial is inappropriate, the trial plan is violated, or for administrative and/or other safety reasons. Specific details regarding discontinuation or withdrawal procedures; including specific details regarding withdrawal from Future Biomedical Research, are provided in Section 7.1.4 – Other Procedures.

Discontinuation from treatment is "permanent". Once a subject is discontinued, he/she shall not be allowed to restart treatment

Protocol/Amendment No.: 004-02

A subject must be discontinued from the trial for any of the following reasons:

• The subject withdraws consent.

(i.e., does not agree to any follow-up)

Note: Since follow-up health status information is important to the full evaluation of any new agent in development, including MK-8521, the investigator should determine if a subject who no longer agrees to actively participate (i.e., no longer attend visits at the investigational site, take blinded investigational product/open-label liraglutide, and have other study-related procedures conducted at the investigational site) is agreeable to providing additional follow-up information through interval telephone contacts (with the site collecting only important health status information (e.g., SAEs). Subjects who agree to follow-up contacts should be discontinued due to "Subject decision to stop active participation" (see 5.9 criteria "1" below), and not "withdrawal of consent." See Section 5.9.1 for additional details about monitoring subjects who discontinue treatment with blinded investigational product/open-label liraglutide.

5.9 Subject Withdrawal/Discontinuation from Treatment Criteria

Discontinuation from treatment is "permanent". Once a subject is discontinued, he/she shall not be allowed to restart treatment. As outlined below, subjects who no longer wish to participate may be withdrawn from active participation, but followed in the trial, or withdrawn from the trial (i.e., no ongoing follow-up), as described below.

A subject must be discontinued from treatment (but may continue to be monitored in the trial) for any of the following reasons:

1. Subject's decision to stop active participation: Subject no longer agrees to actively participate in the study (i.e., take double-blind study medication/open-label liraglutide or other required concomitant study medication, attend study visits, or otherwise comply with study procedures), but agrees to allow follow-up contact. Subject will be contacted at times of regular study visits to collect status (i.e., SAEs), unless the subject specifically withdraws consent for follow-up.

Note: If a subject indicates his or her intention to stop active participation in the trial (i.e., chooses to no longer attend visits at the investigational site, take investigational product, and have other study-related procedures conducted at the investigational site), the investigator must clarify with the subject if he/she is willing to continue in the study with contact at intervals (as described above) to provide a brief and focused update on health status (e.g., evaluate if the subject experienced any SAEs). It will be essential for the subject to understand the importance of complete collection of information, and also the limited requirements for continuing to provide this information (i.e., a brief telephone contact occurring at the time of the originally planned study visits). Thus, subjects may discontinue investigational product and continue in the study with telephone calls or they may indicate that they do not wish to have further contact with the site (i.e., withdrawal of consent).

Protocol/Amendment No.: 004-02

2. Hyperglycemia:

Subject meets (repeated and confirmed) glycemic thresholds specified in Table 7 for the specific time point in the trial, without a reasonable explanation (e.g., intercurrent illness or medication omission).

Table 7 Glycemic Thresholds For Discontinuation

Visit Interval	Glycemic Thresholds (Fasting plasma glucose [FPG])
After Visit 3/Day 1 through Visit 8/Week 6:	FPG consistently >270 mg/dL (15.0 mmol/L)
After Visit 8/Week 6 through Visit 10/Week 12:	FPG consistently >240 mg/dL (13.3 mmol/L)

Note: A consistent value for FPG is defined as a repeat measurement performed within 7 days of notification from the central laboratory. Site should reinforce diet/exercise counseling prior to repeat measurement.

- 3. Hypoglycemia: Repeated (2 or more episodes since the prior visit) FPG or fingerstick glucose
 - <50 mg/dL (<2.8 mmol/L) with or without symptoms of hypoglycemia, or
 - ≤70 mg/dL (≤3.9 mmol/L) with symptoms of hypoglycemia, and without a reasonable explanation (such as increased physical activity or skipped meal) or with a reasonable explanation and likely to reoccur.

Note: The investigator should make sure that the subject's glucose meter and test strips are functioning accurately and that the test procedure is being correctly performed by the subject prior to discontinuation.

- 4. Abnormal liver function tests meeting criteria specified below (see the Management of Subjects with Elevated Liver Enzymes [ALT or AST ≥3X ULN] guidance document in the Investigator Trial File Binder [ITFB] for additional details on management and discontinuation of investigational product for subjects with elevated liver enzymes):
 - ALT or AST $\ge 3X$ ULN with total bilirubin (TBL) $\ge 2X$ ULN and alkaline phosphatase (ALP) < 2X ULN and without an established etiology; or
 - ALT or AST $\geq 8X$ ULN or $\geq 3X$ ULN with symptoms consistent with liver injury and without an established etiology; or
 - ALT or AST \geq 5X ULN for 2 weeks or longer; or
 - ALT or AST ≥3X ULN and subject is unwilling or unable to undergo repeat ALT and AST testing at the frequency defined in the Management of Subjects with Elevated Liver Enzymes (ALT or AST ≥3X ULN) guidance document.
- 5. Elevation in circulating serum lipase $\ge 3X$ ULN that is associated with clinical evidence of pancreatitis (e.g., symptoms of nausea/vomiting, abdominal pain).

Protocol/Amendment No.: 004-02

6. Parameters of Renal Function

• Serum creatinine concentrations consistently ≥ 1.5 mg/dL (133 μ mol/L) in men or ≥ 1.4 mg/dL (124 μ mol/L) in women.

• eGFR consistently <45 mL/min/1.73 m² (MDRD formula).

Note 1: A consistent value is defined as a repeat measurement performed within 7 days of notification from the central laboratory.

Note 2: If the eGFR or serum creatinine value continues to meet discontinuation criterion but demonstrates improvement relative to the prior result, an additional repeat may be performed (within 7 days). If this repeat continues to meet the discontinuation criteria, the subject must be discontinued from investigational product.

7. Has HR increases as detailed below:

Note: Heart rate assessments are based on mean of three consecutive values assessed as detailed in Section 7.1.2. See Section 7.1.2 for detailed HR monitoring instructions

 Tachycardia (mean sitting HR >100 bpm) of any duration associated with symptoms that the study investigator considers potentially related to cardiac ischemia, congestive heart failure and/or hemodynamic compromise. Concerning symptoms might potentially include chest discomfort, chest pain, shortness of breath, and/or lightheadedness.

Note: Subjects with a minimally symptomatic event, non-sustained or recurrent, not meeting other criteria may be continued.

• Sustained mean resting HR >100 bpm measured in the sitting position (sustained defined as continuing after 30 minutes and after 60 minutes of rest in a sitting position: if the 30-minute mean HR is <100, reassessment after 60 minutes should not be done, and reassessment should be performed after 24 hours (see note below)).

Note: If mean HR >100 and \leq 120 or if HR decreases during the 30 minute (or 60 minute) follow up to <100 bpm the dose of investigational product may be administered and the subject will be asked to return for repeat measurement within 24 hours. If mean HR is still >100 after 24 hours, the subject should be discontinued from the study medication.

• Sustained increase from baseline in mean resting HR ≥30 bpm measured in the sitting position (sustained defined as continuing after 30 minutes and after 60 minutes of rest in a sitting position) that persists for ≥2 weeks. If the 30-minute mean HR is <30 bpm higher than baseline, the 60-minute repeat does not need to be performed and the subject may continue in the trial.

Protocol/Amendment No.: 004-02

Note: An ECG should be conducted if a subject is suspected of meeting one of the HR discontinuation criteria detailed above. The ECG should be interpreted by the PI to confirm the measured HR and to diagnose any potential cardiac rhythm or rate abnormality. If confirmed, the discontinuation visit should be performed including an ECG.

- 8. Requirement for one of the prohibited medications listed in Section 5.5.
- 9. Develops any condition for which metformin is contraindicated.
- 10. For subjects randomized to MK-8521 or placebo, subject cannot tolerate at least 0.3 mL from each vial (i.e., 180 μg/day dose for subjects on active MK-8521). For subjects randomized to open-label liraglutide, subject cannot tolerate at least 1.2 mg/day dose.
- 11. For subjects randomized to open-label liraglutide, develops any condition for which liraglutide is contraindicated.

12. Pregnancy

Note: A positive urine pregnancy test requires immediate interruption of blinded investigational product until serum β -hCG can be performed and found to be negative. If pregnancy is confirmed by a positive serum pregnancy test, subject must be permanently discontinued, and pregnancy should be reported and followed per Section 7.2.2.

- 13. Any medical condition or personal circumstance which, in the opinion of the investigator, exposes the subject to risk by continuing investigational product or study procedures or does not allow the subject to adhere to the requirements of the protocol.
- 14. Subject undergoing bariatric surgery.
- 15. For subjects randomized to double-blind investigational product (i.e., MK-8521 or matching placebo), the investigator or subject becomes unblinded to the subject's treatment assignment (i.e., through the IVRS system or emergency unblinding call center).

The Sponsor should be contacted immediately when a subject is discontinued from investigational product or investigational product is interrupted because of any SAE or AE assessed by the investigator as related to investigational product or laboratory abnormality assessed by the investigator as related to investigational product. The Sponsor should also be immediately contacted when a subject is discontinued from investigational product due to HR criteria (see Section 7.2.3.2 for reporting of Events of Clinical Interest).

In this trial, a subject may discontinue investigational product for any of the reasons listed above (items #1 through 15) but continue to participate in the trial (with follow-up contacts), as long as the subject does not withdraw consent. Follow-up procedures for subjects who discontinue investigational product are described in Section 5.9.1.

Protocol/Amendment No.: 004-02

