8.2.9 Interim Analyses

8.2.9.1 Triggered Safety Review for Discontinuation Due to HR

In the event of ≥ 5 subjects discontinuing blinded investigational product (MK-8521 or matching placebo) due to meeting the defined discontinuation criteria for an increase in HR, a review of unblinded safety data by a Standing Internal Data Monitoring Committee will be triggered. For further details on the siDMC, see Section 7.3.2. Review criteria will be provided in the siDMC charter.

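### Section 5.9 gives two rules for a sustained heart rate of 101-120 bpm, so the count that triggers unblinded safety review can depend on how a site reads it

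*Combined protocol and SAP*

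**What the plan says.** The list in Section 5.9 opens with "A subject must be discontinued from treatment (but may continue to be monitored in the trial) for any of the following reasons". The same section makes discontinuation permanent.

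Item 7, second bullet, gives this reason: "Sustained mean resting HR >100 bpm measured in the sitting position (sustained defined as continuing after 30 minutes and after 60 minutes of rest". It sets no upper limit on heart rate. One branch is carved out: "if the 30-minute mean HR is <100, reassessment after 60 minutes should not be done, and reassessment should be performed after 24 hours (see note". The pointer to the note is attached to that branch only.

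The note has two conditions joined by an or. The first is a mean HR above 100 and at or below 120, with no measurement time. The second is "or if HR decreases during the 30 minute (or 60 minute) follow up to <100 bpm". In either case "the dose of investigational product may be administered and the subject will be asked to return for repeat measurement within 24 hours". It then adds: "If mean HR is still >100 after 24 hours, the subject should be discontinued from the study medication".

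Four other places depend on this criterion:

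- Section 4.2.3.2 restates it as a sustained resting HR above 100 bpm and refers to Section 5.9. It mentions no 120 bpm limit and no 24-hour step.
- Section 7.2.3.2 makes any subject who meets the HR discontinuation criteria an Event of Clinical Interest, reportable within 24 hours.
- Sections 8.1.4 and 8.2.9.1 trigger an unblinded siDMC review when 5 or more subjects are "discontinuing blinded investigational product (MK-8521 or matching placebo) due to meeting the defined discontinuation criteria for an increase in HR".

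**The concern.** A subject at 110 bpm at the first reading, at 30 minutes and at 60 minutes meets the bullet and must stop treatment for good. The same subject fits the note's first condition and may be dosed and sent home for a recheck. Both texts are current, and no sentence ranks one above the other.

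This matters because the trial acts on the criterion. It decides whether a subject stays on drug for the rest of the 12 weeks, whether an Event of Clinical Interest is reported, and whether the subject adds to the count of 5. After a triggered review, Section 4.2.3.2 allows the siDMC to stop the study, or to stop or modify an arm. A count pooled over sites needs one event definition.

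**Working it through.** **The plan's own figure.** Section 4.2.3.2 describes 5 discontinuations as potentially more than 10% of one arm. Section 8.2.7 gives 40 subjects per arm: 5/40 = 12.5%, and 4/40 = 10.0% is not above 10%. The trigger of 5 agrees with its stated basis. It is counted over the three blinded arms, 3 × 40 = 120 subjects.

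**The two readings on the same heart rates.** Reading A applies the bullet as written. Reading B treats the note as an exception for a sustained rate of 101-120 bpm.

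| Mean HR at 0 / 30 / 60 min, then at 24 h | Reading A | Reading B | What differs |
|---|---|---|---|
| 110 / 110 / 110, then 95 | discontinue | continue | final outcome |
| 110 / 110 / 110, then 110 | discontinue at the visit | discontinue at the recheck | timing, possibly one dose |
| 125 / 125 / 125, then 95 | discontinue | discontinue | nothing |
| 110 / 95 / not done, then 95 | continue | continue | nothing |

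So the final count differs only for subjects sustained at 101-120 bpm whose rate is no longer above 100 at 24 hours.

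**Recheck time.** The bullet places the reassessment after 24 hours, the note asks for it within 24 hours, and the note's last sentence acts on the rate after 24 hours. A recheck at 20 hours meets the second wording but not the other two. A 30-minute mean of exactly 100 is also covered by neither the above-100 nor the below-100 branch.

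**What this could do to the trigger (illustration only).** The documents give neither rate needed, so both are assumed:

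- p: share of the 120 blinded subjects with a sustained rate of 101-120 bpm at some visit.
- q: share of those who are above 100 at a 24-hour recheck, taken over the whole treatment period.

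Subjects are treated as independent with one common rate, and no other HR discontinuations are counted. With r = p under Reading A and r = p × q under Reading B,

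P(5 or more) = 1 − Σ (k = 0 to 4) C(120, k) r^k (1 − r)^(120 − k).

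| p | Reading A | B, q = 0.25 | B, q = 0.50 | B, q = 0.75 |
|---|---|---|---|---|
| 2% | 9% | <0.1% | 0.7% | 3.5% |
| 4% | 53% | 0.7% | 9% | 29% |
| 6% | 85% | 3.5% | 29% | 63% |
| 8% | 97% | 9% | 53% | 85% |

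For example, p = 4% and q = 0.50 give r = 2%, so Reading B has the same 9% as Reading A at p = 2%. If sites differ in their reading, the probability lies between the two columns. If q is close to 1, the readings nearly agree.

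**The case against.** The strongest reply is that the two texts can be harmonised. The note sits directly under the bullet and is the more specific. Read as an exception, it gives 101-120 bpm a recheck path and leaves sustained rates above 120 bpm to the bullet. Otherwise its 120 bpm limit has little purpose, since a rate that falls below 100 has its own clause. Section 4.2.3.2 is a summary that also omits the two-week persistence condition for the rise of 30 bpm or more, so its silence does not settle the matter. This reading is plausible, but no sentence states it, and the bullet's pointer to the note belongs to a different branch. What stands is that sites can differ. That they will differ is an inference the documents do not support.

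The effect on oversight is also limited. The trigger prompts a review and is not a stopping boundary. Other signals can trigger a review (Section 8.1.4), heart rate is examined at the planned interim analysis, and the Tier 2 heart rate endpoints do not use the discontinuation rule. The sponsor is told at once of each HR discontinuation. That helps only in part: a subject kept on treatment under the note would not be regarded as meeting the criterion, so need not be reported.

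Two stronger statements are tempting. A reader might take the mean rises of about 7 and 8.3 bpm in Section 4.2.2 and infer that enough subjects fall in the disputed band to sit near the trigger of 5. Those rises are placebo-adjusted 24-hour averages, whereas the trial uses seated readings before that day's dose. The documents give no baseline distribution or spread, a single reading above 100 is not a sustained one, and Section 4.2.3.2 expects a low rate of HR discontinuations. A reader might also call heart rate the leading safety concern; Section 4.1.2.2 names it alongside GI intolerance without ranking them.

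**Conclusion.** The conflict is real and lies in the current text of Section 5.9. For a sustained mean heart rate of 101-120 bpm, the bullet requires permanent discontinuation, while the note permits dosing and makes discontinuation depend on a recheck whose time is worded inconsistently. Outcomes differ for subjects whose rate is no longer above 100 at 24 hours. For the others only timing, and possibly one further dose, differs. The Event of Clinical Interest and the siDMC trigger both rest on this criterion, so both counts can depend on site interpretation.

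The size is unknown. Under the assumed rates above, the difference in the probability of reaching 5 ranges from about 5 percentage points (p = 2%, q = 0.75: 9% against 3.5%) to over 80 (p = 8%, q = 0.25 or p = 6%, q = 0.25). These figures show only that the wording can matter; they do not forecast this trial. The point is a wording conflict in a rule the trial acts on. It should be corrected, but it does not put the trigger's design or the choice of 5 in question.

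**What to change.** Reconcile the bullet and the note in Section 5.9, item 7, so that one definition covers a mean heart rate of 101-120 bpm. It should name the measurement times at which that range is judged, say whether the note qualifies the bullet, and give one recheck time. Align the restatement in Section 4.2.3.2. Let Sections 7.2.3.2, 8.1.4 and 8.2.9.1 refer to Section 5.9 and not repeat the rule; 7.2.3.2 already does so. If any HR discontinuations or rechecks have already occurred, classify them under the reconciled definition before counting towards 5.

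Which rule applies is for the sponsor's clinicians to decide. The cost is protocol wording and a notice to sites.
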